## **7.0 TRIAL PROCEDURES**

### **7.1 Trial Procedures**

The Trial Flow Chart - Section 6.0 summarizes the trial procedures to be performed at each visit. Individual trial procedures are described in detail below. It may be necessary to perform these procedures at unscheduled time points if deemed clinically necessary by the investigator.

Furthermore, additional evaluations/testing may be deemed necessary by the investigator and or the Sponsor for reasons related to subject safety. In some cases, such evaluation/testing may be potentially sensitive in nature (e.g., HIV, Hepatitis C, etc.), and thus local regulations may require that additional informed consent be obtained from the subject. In these cases, such evaluations/testing will be performed in accordance with those regulations.

#### **7.1.1 Administrative Procedures**

##### **7.1.1.1 Informed Consent**

The investigator must obtain documented consent from each potential subject prior to participating in a clinical trial or Future Biomedical Research.

###### **7.1.1.1.1 General Informed Consent**

Consent must be documented by the subject's dated signature or by the subject's legally acceptable representative's dated signature on a consent form along with the dated signature of the person conducting the consent discussion.

A copy of the signed and dated consent form should be given to the subject before participation in the trial.

The initial informed consent form, any subsequent revised written informed consent form and any written information provided to the subject must receive the IRB/ERC's approval/favorable opinion in advance of use. The subject or his/her legally acceptable representative should be informed in a timely manner if new information becomes available that may be relevant to the subject's willingness to continue participation in the trial. The communication of this information will be provided and documented via a revised consent form or addendum to the original consent form that captures the subject's dated signature or by the subject's legally acceptable representative's dated signature.

Specifics about a trial and the trial population will be added to the consent form template at the protocol level.

The informed consent will adhere to IRB/ERC requirements, applicable laws and regulations and Sponsor requirements.

#### **7.1.1.1.2 Consent and Collection of Specimens for Future Biomedical Research**

The investigator or qualified designee will explain the Future Biomedical Research consent to the subject, answer all of his/her questions, and obtain written informed consent before performing any procedure related to the Future Biomedical Research sub-trial. A copy of the informed consent will be given to the subject.

#### **7.1.1.2 Inclusion/Exclusion Criteria**

All inclusion and exclusion criteria will be reviewed by the investigator or qualified designee to ensure that the subject qualifies for the trial. Diagnosing the deep-seated fungal infection and identifying the infected site will be appropriately recorded in the source document and eCRF.

#### **7.1.1.3 Subject Identification Card**

All subjects will be given a Subject Identification Card identifying them as participants in a research trial. The card will contain trial site contact information (including direct telephone numbers) to be utilized in the event of an emergency. The investigator or qualified designee will provide the subject with a Subject Identification Card after the subject provides written informed consent.

#### **7.1.1.4 Medical History**

A medical history will be obtained and recorded by the investigator or qualified designee.

#### **7.1.1.5 Prior and Concomitant Medications Review**

##### **7.1.1.5.1 Prior Medications**

The investigator or qualified designee will review prior medication use, including any protocol-specified washout requirement, and record the anti-fungal drug taken by the subject within 30 days before starting the study treatment, anti-bacterial drug taken by the subject within 14 days before starting the study treatment and record any other prior medication taken by the subject within 3 days before starting the study treatment.

##### **7.1.1.5.2 Concomitant Medications**

The investigator or qualified designee will record medication, if any, taken by the subject during the trial.

#### **7.1.1.6 Assignment of Screening Number**

All consented subjects will be given a unique screening number that will be used to identify the subject for all procedures that occur prior to randomization or treatment allocation. Each subject will be assigned only one screening number. Screening numbers must not be re-used

for different subjects. Any subject who is screened multiple times will retain the original screening number assigned at the initial screening visit.

#### **7.1.1.7 Assignment of Randomization Number**

All eligible subjects will be randomly allocated to trial treatment and will receive a randomization number. The randomization number identifies the subject for all procedures occurring after randomization. Once a randomization number is assigned to a subject, it can never be re-assigned to another subject.

A single subject cannot be assigned more than 1 randomization number.

#### **7.1.1.8 Trial Compliance (Medication/Diet/Activity/Other)**

Interruptions from the protocol specified treatment plan for 4 days require consultation between the investigator and the Sponsor and written documentation of the collaborative decision on subject management.

In case of administration of trial medication (IV formulation), administration will be witnessed by the investigator and/or trial staff.

In case of administration of trial medication (oral formulation), the way of the administration of trial medication will be informed to the subjects by the investigator and/or designee. The investigator and/or designee provides the direction that trial medication and meal should be recorded in the medication diary. The subjects bring the medication diary when subjects visit the hospital, and the medication diary will be confirmed by the investigator and/or designee. The medication diary is stored at the study site after the clinical trial. All the information of trial medication and meal should be recorded in the source document and eCRF.

### **7.1.2 Clinical Procedures/Assessments**

In order to minimize variability, it is preferred that the same individuals perform the same procedures/evaluations for all subjects at each trial site.

#### **7.1.2.1 Physical Examination**

Physical examination is performed at the specified visit and recorded in the source document. In case of abnormal physical findings compared to the baseline after the initiation of study treatment, the investigator/sub-investigator assesses and records whether the physical findings are adverse event, or not in the source document and eCRF.

#### **7.1.2.2 Clinical Signs and Symptoms of Deep-Seated Fungal Infection**

Attributable clinical signs and symptoms of deep-seated fungal infection [cough, dyspnea, sputum, bloody sputum, hemoptysis, pain, pyrexia and weight decreased etc.] are identified, and assessed through the existence and severity of vital signs and shifts of clinical laboratory

values (CRP etc.) for reference and recorded in the source document and eCRF at the scheduled visit. Intensity is evaluated in the following criteria.

Absense: There is no symptom or observation.

Mild: Grade 1 symptom or observation defined by the CTCAE grading (version 4.0).

Moderate: Grade 2 symptom or observation defined by the CTCAE grading (version 4.0).

Severe: Grade 3(or more) symptom or observation defined by the CTCAE grading (version 4.0).

#### **7.1.2.3 Vital Signs**

Temperature (oral, axilla or archo), pulse, blood pressure, weight and SpO2 will be measured and recorded in the source document and eCRF at the scheduled visit. If it is difficult to measure these testing based on the subject's condition, it may not be done. Temperature recorded should be highest (maximum temperature) in each day. In principle, measuring method is same throughout the study. If the temperature is measured other than scheduled visit during the study, all of these data should be recorded in the source document and eCRF.

#### **7.1.2.4 12-Lead Electrocardiogram**

12-lead electrocardiogram is performed using standard equipment that can be measured for ventricular rate, RR, PR, QRS, QT and QTc interval. 12-lead electrocardiogram is performed at the scheduled or unscheduled visit and tried to measure at the time of the highest plasma concentration. Serum electrolytes (K, Ca, Mg) must be measured on the same day and recorded in the source document and eCRF, in case an unscheduled 12-lead electrocardiogram is performed. Clinically abnormal findings in the electrocardiogram will be followed up until recovering to the baseline value or stabilization appropriately. If QTc interval is greater than 500 msec, study treatment must be discontinued.

#### **7.1.2.5 Diagnostic Imaging**

The type of imaging used (e.g. CT or MRI) will depend on the site of infection. For pulmonary sites of infection, CT scanning is required. Each site of infection identified during screening should be followed throughout the study by repeating the same type of scan and the same imaging modality. Imaging must be performed at the scheduled visit and all imaging must be recoded and stored at the study site appropriately, and masked imaging is provided to the sponsor or the designated imaging facility. In case of performing imaging at the unscheduled visit, the masked imaging may be provided to the sponsor or the designated imaging facility by the direction of clinical adjudication committee or trial physician for the assessment. The imaging at the unscheduled visit also must be recoded and stored at the study site appropriately. In addition, imaging performed in the time when the subject condition was good and antifungal treatment was not needed may be provided to the sponsor or the designated imaging facility after being masked by the direction of clinical adjudication committee or trial physicians for the assessment.

#### **7.1.2.6 Mycology Testing**

Mycology testing is performed and fungal infection is observed by using the appropriate method. Even if causative fungus is identified by mycological serology testing, direct microscopy or histopathological examination, culture testing must be performed. Causative fungus is isolated from culture sample and its genus is identified at the study site. Fungal infection is followed throughout the trial by repeating the same mycology testing based on subjects' condition in principle. The fungus isolated by culture testing is provided to the central laboratory and its species is identified and minimum inhibitory concentration (MIC) testing is performed at the central laboratory. At the study site, isolated fungus is appropriately stored until identification of species. If the fungus isolated by culture testing done at the time other than the specified visit in the protocol, this is also provided to the central laboratory and isolated fungus is appropriately stored at the study site until identification of species.

If the microorganisms other than fungus are isolated by culture testing, all of these data should be recorded in the source document and eCRF appropriately.

#### **7.1.2.7 Serology Testing (Aspergillus Antigen, Aspergillus Antibody and $\beta$ -D-Glucan)**

Aspergillus antigen, antibody and  $\beta$ -D-glucan are measured at the scheduled visit and their result is recorded in the source document and eCRF appropriately. Aspergillus antibody is measured at the screening only. If the aspergillus antigen and  $\beta$ -D-glucan are measured at the unscheduled visit, all of these data should be recorded in the source document and eCRF appropriately. This testing does not need to be measured for the subjects with fusariosis and zygomycosis.

#### **7.1.2.8 Sample Collection for Plasma Concentration of MK-5592 (MK-5592 Treatment Arm)**

Blood sample for plasma concentration of MK-5592 is collected on the scheduled visit. Volume of the blood sampling is 2 mL/time. Blood sampling must be collected via other location different from the location of study administration. Regarding the sampling points of just before the end of first infusion on Day 1 and 8 for MK-5592 IV solution, blood sampling should be done before flushing. From the feasibility point of view, blood sampling after the treatment on Day 1 (IV solution: just before the end of first infusion, 6 to 10 hours after the initiation of the infusion and just before the treatment of second infusion, solid oral tablet: 2 to 4 hours after the first treatment, 6 to 10 hours after the treatment and just before the second treatment) can be performed after the second dosing if it is difficult to perform the blood sampling after the first dosing (e.g. in case that the first dose is in the night). If it is difficult to perform the blood sampling at the just before the second treatment/infusion, it may not be done but the reason for not performing the blood sampling must be recorded in the source document and eCRF. Blood sampling after the first dosing on Day 1 (or second dosing) should be performed at least 3 hours apart among these sampling points (IV solution: 6 to 10 hours after the initiation of the infusion and just before the treatment of second infusion, solid

oral tablet: 6 to 10 hours after the treatment and just before the second treatment). Sampling date and time must be correctly recorded in the source document and eCRF.

#### **7.1.2.9 Evaluation for Overall Response**

The individual response assessment (Clinical Response, Radiological Response, Mycological Response and Clinical Laboratory Response) in subjects with deep-seated fungal infection will be evaluated at Day 42, EOT(before the transition to the extension period) and switching formulation according to the criteria described in 4.2.3.1, and Overall Response is assessed based on these individual responses (However, if the subject is a patient with zygomycosis and joins the extension period, the individual response assessment at switching formulation or the last dose of MK-5592 therapy in the extension period does not need to be done). Overall response assessed by investigator and information are provided to the Clinical adjudication committee. CAC assessed the overall response according to the same criteria. The assessment by CAC is used as a Primary efficacy endpoint.

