#### **4.2.3 Rationale for Endpoints**

Safety and efficacy endpoints in this study are based on the EORTC/MSG criteria [14, 15], endpoints of MK-5592 clinical study conducted outside Japan, endpoints of clinical study for chronic pulmonary aspergillosis conducted in and outside Japan [16, 17], and the guideline as antifungal drugs evaluation committee by Japan chemotherapy association March 2012 [18]. Deep-seated fungal infection is usually manifested in immunocompromised subjects with serious underlying diseases (such as HIV, organ transplantation, and cancer). For such infections, the assessment of efficacy usually takes into consideration a number of key variables, including the response to clinical signs and symptoms (Clinical Response), the response to mycological measures of the infection (Mycological Response), and the response to radiological evidence of the infection (Radiological Response). Therefore, an overall response, which encompasses many of these individual components, is routinely applied to the assessment of efficacy in these types of infections. Overall response criteria for invasive aspergillosis is set in 5 levels (complete response, partial response, stable response, progressive disease and unable to determine). Success is defined as complete response and partial response. Failure is defined as stable response, progressive disease and unable to determine. Overall response criteria for chronic pulmonary aspergillosis is set in 4 levels (favorable response, stable response, progressive disease and unable to determine). Success is defined as favorable response. Failure is defined as stable response, progressive disease and unable to determine. For chronic pulmonary aspergillosis, it is rare that ‘finding of imaging’ are resolved. Complete response and partial response are not set but favorable response is set in overall response. The overall response is evaluated by the investigator or sub-investigator according to the criteria. The overall response is finally evaluated by the clinical adjudication committee.

For subject with IA, we set the endpoint at Day 42 same as global study (069 study) in order to be able to confirm the efficacy between 101 and 069 study. For subject with CPA, we set the endpoint at Day 84 same as registration clinical studies conducted with using other anti-fungal drugs in the subject with CPA in Japan.

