### **5.2.3 Trial Blinding/Masking**

This is an open-label trial; therefore, the Sponsor, investigator and subject will know the treatment administered.

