## **7.3 TRIAL GOVERNANCE AND OVERSIGHT**

### **7.3.1 Clinical Adjudication Committee**

A Clinical Adjudication Committee (CAC) will evaluate the following events for the purposes of confirming them according to the criteria in Section 8.0 – Statistical Analysis Plan.

- 1) Diagnosis of deep-seated fungal infection [For subjects with all queries closed, validity of deep-seated fungal infection diagnosed by investigators is assessed]
- 2) Overall Response [For subjects with all queries closed, validity of Overall Response assessed by investigator is assessed (Overall Response, Clinical Response, Radiological Response, Mycological Response)]

All personnel involved in the adjudication process will remain blinded to treatment allocation throughout the trial. Specific details regarding endpoint definitions can be found in the Adjudication Charter.

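### The blinded adjudication committee is given the open-label investigator's response rating and asked to assess its validity; neither protocol nor SAP has the committee rate first, so borderline calls in the primary efficacy endpoint are exposed to arm knowledge

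*Combined protocol and SAP*

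**What the plan says.** Section 5.2.3 states that "the Sponsor, investigator and subject will know the treatment administered". Section 7.1.2.9 then describes how the rating reaches the CAC: "Overall response assessed by investigator and information are provided to the Clinical adjudication committee". The next sentence says "CAC assessed the overall response according to the same criteria", and the section makes the CAC's assessment the primary efficacy endpoint.

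Section 7.3.1 describes the CAC's job differently: "For subjects with all queries closed, validity of Overall Response assessed by investigator is assessed". It lists the overall, clinical, radiological and mycological responses under that task. Section 4.2.3 has the investigator evaluate overall response and adds that "The overall response is finally evaluated by the clinical adjudication committee".

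The safeguards in the text are these:

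- Section 7.3.1: "All personnel involved in the adjudication process will remain blinded to treatment allocation throughout the trial".
- SAP sections 8.2.1 and 8.2.3.3: the CAC works blinded, on data with information masked. Treatment assignment is the one example named.
- Section 7.1.2.5: "masked imaging is provided to the sponsor or the designated imaging facility". This sentence does not itself say that the images go on to the CAC. That the CAC receives masked data comes from 8.2.3.3.

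On procedure, 7.3.1 refers outwards: "Specific details regarding endpoint definitions can be found in the Adjudication Charter".

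**The concern.** In an open-label trial, a blinded committee is there to produce a rating that does not depend on knowing the arm. Masking the treatment label does not remove arm knowledge already contained in a rating made by someone who knew the arm. If a committee member has that rating in view when deciding a close case, the decision may lean towards it.

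Two things are at stake. The first is the response-rate estimates for the primary efficacy endpoint. The second is the value of the planned supportive analysis on investigator ratings (8.2.5.1.2). If the CAC saw those ratings before deciding, disagreement between the two remains informative, but agreement may be partly built in.

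**Working it through.** **1. What the text fixes and what it leaves open.**

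- Is the investigator's overall rating sent to the CAC? Yes (7.1.2.9).
- What does the CAC do with it? It assesses its validity (7.3.1) and also rates by the same criteria (7.1.2.9).
- Is the rating masked or withheld? No section says so. The masking wording in 8.2.1 and 8.2.3.3 is open-ended, but withholding the rating altogether would contradict 7.1.2.9 and 7.3.1.
- Does the CAC record its own rating first? No section says so. The word used in 4.2.3 can mean only that the CAC's rating is the definitive one.

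**2. Where a judgement can change the result.** In CPA, overall response combines the clinical and radiological components (Table 11), and success means Favorable Response. Take one component as a close call between Stabilization and Improvement:

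- Other component Improvement: Favorable either way.
- Other component Stabilization: Stable (failure) becomes Favorable (success).
- Other component Worsening: Progressive Disease either way.
- Other component Unable to determine: Unable to determine, hence failure, either way.

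So this call decides success in one of the four situations. Table 7 separates improvement from minor improvement without a threshold, and Table 8 leaves CPA imaging to an overall judgement of size and quality.

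IA leaves less room. Radiological improvement has a 25% diameter rule. With radiology at Stabilization, Table 10 lets mycology settle the case in which clinical response is Improvement.

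**3. Method check on the plan's own figure.** Section 8.2.7 gives lower limits of 46.5% and 67.7% for response rates of 60% and 80% with 60 subjects. The exact (Clopper-Pearson) 95% limits are the 2.5% quantile of Beta(x, n−x+1) and the 97.5% quantile of Beta(x+1, n−x).

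- 36/60: 46.5% to 72.4%.
- 48/60: 67.7% to 89.2%.

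Both lower limits reproduce. However, 60 is the whole MK-5592 arm, whereas the primary endpoint is reported by disease (8.2.3.1.1), so disease-specific denominators are needed for scale.

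**4. Scale of one changed rating.** Inputs from 8.2.7: 90 subjects, 15 with IA, 2:1 allocation. Assumption: all enter the FAS.

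- CPA: 90 − 15 = 75, split 50 and 25. One rating is 100/50 = 2.0 points (MK-5592) or 100/25 = 4.0 points (voriconazole).
- IA: 15 split 10 and 5. One rating is 100/10 = 10 points or 100/5 = 20 points.

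A smaller FAS makes each step larger.

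**5. Against the planned interval, CPA.** Half-widths are from unrounded limits.

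| Successes | 95% CI | Half-width (points) |
|---|---|---|
| 30/50 | 45.2% to 73.6% | 14.2 |
| 40/50 | 66.3% to 90.0% | 11.8 |
| 15/25 | 38.7% to 78.9% | 20.1 |
| 20/25 | 59.3% to 93.2% | 16.9 |

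A single changed rating is well inside these half-widths. They describe sampling error only and would not reflect a systematic lean.

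**The case against.** The strongest reply is that this is a silence in two documents, not a shown defect. The order of rating is ordinary charter material and the Charter has not been seen. The CAC is blinded and uses the same criteria. Section 8.2.3.3 says it works from clinical, radiological and mycological response data, and Table 25 does not list the investigator's overall rating among the inputs. Section 7.1.2.5 lets the CAC call for additional images, which suggests that it reads primary material. Symptoms are graded by CTCAE (7.1.2.2), which gives the clinical component some structure. Efficacy carries no hypothesis or formal test (8.2.2, 8.2.5), and the primary objective is safety.

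Most of this stands as a limit on the size of the problem, but it does not close the route. Section 8.2.3.3 and Table 25 do not say whose component ratings are meant, while 7.3.1 puts the investigator's component ratings before the CAC for a validity check. CTCAE grades describe each symptom but set no threshold between minor improvement and improvement overall. The protocol does more than stay silent: it states that the rating is provided. If the Charter already fixes the order, the remedy shrinks to one sentence.

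A reader might infer that the CAC is effectively unblinded, or that it merely endorses site ratings. The documents do not support either reading: allocation is masked and the CAC applies the criteria itself. A reader might also infer that entry to the FAS is compromised, because the CAC also reviews diagnoses. That is marginal. Entry diagnosis rests on screening before Day 1, leaving only possible IA upgraded within 7 days after randomization. The primary efficacy endpoint is also analysed in the ITT population, which does not depend on CAC diagnosis (8.2.4.1).

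**Conclusion.** The concern holds in a limited form. The protocol supplies an arm-aware rating to the blinded committee, words its task as checking that rating, and neither protocol nor SAP requires an independent rating first. The exposure is confined to borderline calls, mainly the CPA case in which one component is Stabilization and the other lies between Stabilization and Improvement.

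The steps of about 2 and 4 points for CPA and 10 and 20 for IA show what one rating is worth. They are not estimates of bias. They assume that the 15-subject IA target is met, that the 2:1 split holds within each disease and that every subject enters the FAS. The documents give no rate of borderline or discordant calls and no direction, so the bias itself cannot be sized.

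Only the descriptive response rates are affected. No efficacy test depends on them, and the primary safety comparison does not use them. The change is worth making because it is cheap and protects the independence for which the CAC was set up. Confidence is medium, because the Charter could already contain the safeguard.

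**What to change.** State in 7.1.2.9 and 7.3.1, and confirm in the Adjudication Charter, that the CAC records its component and overall response ratings from masked source data before any investigator rating is released to it. Reword the validity task in 7.3.1 to match. Use the investigator's ratings only in the secondary analysis already planned in 8.2.5.1.2, and tabulate CAC–investigator agreement by arm.

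The cost is protocol wording, a Charter check and a small change to the adjudication package and workflow. No new visits, tests or readers are needed, since 8.2.3.1.2 already assigns the component ratings to the CAC. The remedy is partial: the unblinded site still grades signs and symptoms and judges whether they are attributable to the infection (7.1.2.2), and the CAC depends on those data in any case.
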